## C. AIM 3 (MAJOR ADVERSE EVENTS)

What is the frequency of major adverse events following these three different bariatric surgical procedures at 1, 3, and 5 years?

Primary Analysis: Complete three pairwise comparisons (RYGB vs. AGB; RYGB vs. SG; AGB vs. SG) for our primary and secondary outcomes and all sensitivity/heterogeneity analyses on adults  $>20$  years of age using *individual-level data*.

Primary Outcomes: 1) Time until reoperation or re-intervention.

Primary Comparison: Hazard ratio of reoperation/re-intervention for RYGB vs. SG, RYGB vs. AGB, and SG vs. AGB.

Sensitivity Analysis (for primary outcome): 1) include endoscopic procedures in re-intervention definition.

Heterogeneity Analyses (for primary outcome): 1) Compare adults  $<65$  years and 65+ years; 2) Compare Elixhauser comorbidity index score groups ( $<0$ ;  $0$ ;  $>0$ ); 3) Compare baseline BMI (three groups: BMI  $\geq 60$ ,  $60 > BMI >= 50$ , BMI  $< 50$  kg/m $^2$ ); 4) Compare race/ethnicity (e.g., non-Hispanic black, Hispanic, non-Hispanic white); 5) Gender (male vs. female); 6) Diabetes vs no Diabetes.

Secondary Outcomes: 1) Time until mortality (all-cause); 2) Occurrence of composite adverse event (AE) metric derived from the bariatric literature (censored at 30 days); and 3) Time until rehospitalization.

Secondary Comparisons: 1) hazard ratio (HR) for all-cause mortality; 2) odds ratio (OR) for 30-day composite AE; and, 3) HR for rehospitalization for RYGB vs. SG, RYGB vs. AGB, and SG vs. AGB.

## D. AIM 4 (SURGERY OUTCOMES AND BASELINE DEPRESSION)

To what extent do bariatric surgery outcomes explored in Aims 1-3 differ across three bariatric procedures (AGB, RYGB, and SG) with respect to baseline **depression diagnosis** at 1, 3, and 5 years after surgery?

Analyses: Complete heterogeneity in treatment effect (HTE) analyses for three pairwise comparisons (RYGB vs. AGB; RYGB vs. SG; AGB vs. SG) for primary and secondary outcomes from Aims 1-3.

Outcomes (and comparisons):

- (1) Percent total weight loss at 1, 3, and 5 years (difference in percent total weight loss)
- (2) Proportion of patients with >5%, 10%, 20%, and 30% total weight loss (odds ratio)
- (3) Rate of diabetes remission (hazards ratio)
- (4) Rate of relapse after initial remission (hazards ratio)
- (5) Change in HbA1c at 1, 3, and 5 years (difference in change in HbA1c)
- (6) Time until reoperation or reintervention with and without endoscopy (hazards ratio)
- (7) Time until all-cause mortality (hazards ratio)
- (8) Time until hospitalization (hazards ratio)
- (9) Proportion of patients with 30-day composite adverse events (odds ratio)

## E. AIM 5 (SURGERY OUTCOMES AND RACE/ETHNICITY)

To what extent do bariatric surgery outcomes explored in Aims 1-3 differ across three bariatric procedures (AGB, RYGB, and SG) with respect to baseline **depression diagnosis** at 1, 3, and 5 years after surgery?

Analyses: Complete heterogeneity in treatment effect (HTE) analyses for three pairwise comparisons (RYGB vs. AGB; RYGB vs. SG; AGB vs. SG) for primary and secondary outcomes from Aims 1-3.

Outcomes (and comparisons):

- (10) Percent total weight loss at 1, 3, and 5 years (difference in percent total weight loss)
- (11) Proportion of patients with >5%, 10%, 20%, and 30% total weight loss (odds ratio)
- (12) Rate of diabetes remission (hazards ratio)
- (13) Rate of relapse after initial remission (hazards ratio)
- (14) Change in HbA1c at 1, 3, and 5 years (difference in change in HbA1c)
- (15) Time until reoperation or reintervention with and without endoscopy (hazards ratio)
- (16) Time until all-cause mortality (hazards ratio)
- (17) Time until hospitalization (hazards ratio)
- (18) Proportion of patients with 30-day composite adverse events (odds ratio)

## F. AIM 6 (SURGERY OUTCOMES AND MEDICARE AGE)

To what extent do bariatric surgery outcomes explored in Aims 1-3 differ across three bariatric procedures (AGB, RYGB, and SG) with respect to baseline **age 65+ versus <65 years** at 1, 3, and 5 years after surgery?

Analyses: Complete heterogeneity in treatment effect (HTE) analyses for three pairwise comparisons (RYGB vs. AGB; RYGB vs. SG; AGB vs. SG) for primary and secondary outcomes from Aims 1-3.

Outcomes (and comparisons):

- (19) Percent total weight loss at 1, 3, and 5 years (difference in percent total weight loss)
- (20) Proportion of patients with >5%, 10%, 20%, and 30% total weight loss (odds ratio)
- (21) Rate of diabetes remission (hazards ratio)
- (22) Rate of relapse after initial remission (hazards ratio)
- (23) Change in HbA1c at 1, 3, and 5 years (difference in change in HbA1c)
- (24) Time until reoperation or reintervention with and without endoscopy (hazards ratio)
- (25) Time until all-cause mortality (hazards ratio)

- (26)Time until hospitalization (hazards ratio)
- (27)Proportion of patients with 30-day composite adverse events (odds ratio)

## DATA SOURCES

All data for the main scientific aims of this study will be derived from the PCORnet Common Data Model (CDM). The specific CDM tables and variables that are important to this study have been specified in Table 1 below.

### B. EXCLUSION CRITERIA

1. Their first bariatric procedure during the study period is a revision or an uncommon bariatric procedure (see Table 3 below). (Note that patients who have a primary (not revision) bariatric procedure but then subsequently go on to have a revision procedure days or years after their primary procedure will be included in the study.)
2. Those who have multiple bariatric procedures coded on the same day – unable to determine procedure type (see procedure assignment algorithm following Table 2 below)
3. Those whose bariatric procedure occurs the same day as an Emergency Department visit – likely the procedure is a revision and not initial
4. Those who have a non-inpatient or non-ambulatory encounter with a bariatric code.
5. Exclude those with Fundoplasty procedure in year before bariatric procedure.
6. Excluding those who have 1+ gastrointestinal cancer diagnosis codes in year before their bariatric procedure: (ICD-9 150.x, 151.x, 152.x, 157.x, 159.x, 171.5, 209.0x, 209.1x, 209.20, 209.23, 209.25, 209.26, 209.27, 209.29, 209.40-209.43, 209.5x, 209.60, 209.63, 209.65, 209.66, 209.67, 209.69, 211.x, 215.5, 238.1 and 199.x),
7. Those with no BMI measures in year before surgery

8. Baseline information on patient sex is missing or is a category other than "M" or "F" (for example, "U").

### C. ADDITIONAL AIM 2 INCLUSION CRITERIA

For these analyses, eligible patients must have uncontrolled or medication-controlled diabetes at the time of surgery.

1. Hemoglobin A1c (HbA1c)  $\geq 6.5\%$  at the most recent measurement prior to surgery, or
2. Current prescription for diabetes medication at the time of surgery with the most recent HbA1c  $< 6.5\%$ 
  - a. An Insulin and Oral Diabetes Medications List can be found below in Table 4.

Note that Patients taking only metformin will be excluded unless they also have an ICD-9 code for Diabetes (250.x) or have HbA1c  $\geq 6.5\%$  in the year prior to surgery. This includes patients with polycystic ovarian syndrome (PCOS) [2/26/16].

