## B. AIM 2 (IMPROVEMENTS IN DIABETES RISK)

### 1. Primary analysis

The analytic framework for Aim 2 is similar to that described in Aim 1. The primary analysis will have three pairwise comparisons. The primary outcome of interest is: (1) remission from diabetes (a time-to-event outcome), defined as HbA1c <6.5% after 90+ days of not having any active anti-hyperglycemic prescription order or dispensing post-surgery. We will estimate the PSs as described in Aim 1, and fit a Cox proportional hazards model to estimate the effects of surgery on diabetes remission, with a maximum follow-up of 1, 3, or 5 years after surgery [CI-3]. In addition to regression, matching, and weighting considered in Aim 2, PS stratification is also compatible with Cox regression. Specifically, we can fit a stratified Cox regression stratifying on site and site-specific PS percentiles (e.g., deciles). The secondary outcome of interest is the differential impact of the procedures on glycemic control, measured as change in HbA1c from baseline to 1, 3, and 5 years. As this secondary outcome is a continuous variable, our analytic approach will be similar to the one described in Aim 1.

Handling Pregnancy: Because pregnancy events – particularly the third trimester – can have significant effects on glycemic control, we will ignore any HbA1c measures that occur during a pregnancy period, defined as 9 months before and 3 months after any code indicating a full-term delivery, pre-term delivery, miscarriage, or abortion procedure. We will also ignore any HbA1c measurements that occur during an inpatient hospitalization or during a treatment episode for oral steroid medications. We will also ignore diabetes medication use 9 months before and 3 months after any code indicating a full-term delivery, pre-term delivery, miscarriage, or abortion procedure.

Given the nature of the date ranges for the CDM data, we will not likely be able to construct a meaningful measure of Diabetes Duration at the time of surgery.

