## POTENTIAL ADDITIONAL SECONDARY OR EXPLORATORY ANALYSES:

Time and resources permitting, we will consider conducting a number of additional secondary or exploratory analyses for our aims; however, we currently believe that these analyses are either a) beyond the scope of our current proposal, or b) are likely to be challenged by lack of sufficient data to address the question.

- a. It was proposed that we conduct a secondary analysis among patients with a BMI between 30 and 34.9 kg/m^2 because this subgroup is of high interest to the bariatric community, especially as it relates to diabetes outcomes, but also in relation to weight loss and safety.
- b. Look at geographical variation across the US for the 3 procedures
- c. Look at hospital volume and look for correlation with outcomes and complications.
- d. For Aim 3, opportunity to analyze outcomes according to the following designation of centers: low vs. high volume centers, accredited vs non-accredited centers, academic vs community centers, teaching vs non-teaching hospitals.
- e. Consider the impact of people who are on weight loss medications after surgery and what differential impact this may have on our weight loss and diabetes outcomes across procedures, including: phentermine, orlistat (alli/Xenical), lorcaserin (Belviq), phentermine HCL/topiramate ER (Qsymia), Naltrexone HCL/bupropion HCL ER (Contrave), and Liraglutide (victoza and Saxenda). We may want to consider Metformin as well.
- f. For the adolescent group, it may be interesting to compare surgeries at adolescent centers vs. non-adolescent centers, specifically evaluating surgical complications, weight loss, and co-morbidity improvement.

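### The Aim 2 entry rule checks for diabetes in metformin-only users but not in liraglutide users, so patients without diabetes can enter the remission analysis; the effect is probably small and the repair is cheap

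*SAP*

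**What the plan says.** The SAP's Additional Aim 2 Inclusion Criteria state the target population: "eligible patients must have uncontrolled or medication-controlled diabetes at the time of surgery". Two routes put this into practice. Route 1 is a most recent pre-surgery HbA1c of at least 6.5%. Route 2 is "Current prescription for diabetes medication at the time of surgery with the most recent HbA1c" below 6.5%. The drugs that count are set by reference: "An Insulin and Oral Diabetes Medications List can be found below in Table 4". Neither route requires a diagnosis code.

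One note restricts route 2: "Note that Patients taking only metformin will be excluded unless they also have an ICD-9 code for Diabetes (250.x") or an HbA1c of at least 6.5% in the year before surgery. The note mentions polycystic ovarian syndrome.

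Table 4 lists liraglutide by generic name among the non-insulin drugs, with no split by brand or indication. Under Potential Additional Secondary or Exploratory Analyses, item e lists weight-loss medications and ends: "and Liraglutide (victoza and Saxenda). We may want to consider Metformin as well".

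The Aim 2 primary analysis takes remission as the primary outcome, "defined as HbA1c <6.5% after 90+ days of not having any active anti-hyperglycemic prescription order or dispensing post-surgery".

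**The concern.** The metformin note shows that the authors knew a prescription does not by itself establish diabetes. They put a check on the one drug for which they named another use. Elsewhere the same SAP names a second Table 4 drug with another use, liraglutide for weight, and the check was not extended to it. Everyone in this cohort has a BMI of at least 35, so weight is an obvious possible reason for the prescription.

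A patient who enters this way has no diabetes to remit and already meets the HbA1c part of the remission definition. At stake is the meaning of the Aim 2 primary outcome. Two further effects follow from the definitions:

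- Relapse includes restarting medication, so resuming liraglutide for weight after a counted remission could be recorded as diabetes relapse.
- The Aim 2 criteria are carried into Aims 4-6 for the same outcomes, so the gap travels with them.

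**Working it through.** **Rule trace.** Take a patient with BMI of at least 35, no 250.x code, every HbA1c below 6.5%, and a current liraglutide prescription at surgery.

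1. Route 1 (HbA1c at least 6.5%): not met.
2. Route 2 (current Table 4 drug, most recent HbA1c below 6.5%): met, because liraglutide is in Table 4.
3. Metformin note: does not apply, because the patient is not taking only metformin. The same holds for a patient without diabetes on metformin plus liraglutide.
4. Result: the patient enters Aim 2.
5. Remission: if the drug is stopped, and an HbA1c below 6.5% is recorded after at least 90 days with no active order or dispensing, the patient is counted as remitted. Without such a measurement the patient is not counted.

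**Size.** The SAP gives no Aim 2 sample size, remission rate or count of such patients, so there is no stated figure to reproduce. All inputs below are assumptions:

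- q: share of the Aim 2 cohort without diabetes and on liraglutide, 0.5% to 5%
- p: true remission proportion, 0.30 to 0.60
- m: share of those liraglutide users who end up counted as remitted, 0.70 to 0.95

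Apparent remission is o = (1 − q)p + qm, so the shift is o − p = q(m − p). The smallest shift is at p = 0.60, m = 0.70. The largest is at p = 0.30, m = 0.95.

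| q | smallest shift, q × 0.10 | largest shift, q × 0.65 |
|---|---|---|
| 0.5% | 0.05 points | 0.32 points |
| 1% | 0.10 points | 0.65 points |
| 2% | 0.20 points | 1.30 points |
| 5% | 0.50 points | 3.25 points |

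Aim 2 reports a Cox hazard ratio, so the more relevant scale is the ratio of cumulative hazards, ln(1 − o)/ln(1 − p). Put the whole share in one procedure group and none in the other, with equal true remission p = 0.50 and m = 0.95:

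| q | o | apparent HR when the true HR is 1.00 |
|---|---|---|
| 0.5% | 0.5023 | 1.007 |
| 1% | 0.5045 | ln(0.4955)/ln(0.5) = 1.013 |
| 2% | 0.5090 | ln(0.4910)/ln(0.5) = 1.026 |
| 5% | 0.5225 | ln(0.4775)/ln(0.5) = 1.066 |

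This treats hazards as constant within each group, so it approximates the fitted Cox estimate. Placing the whole share in one group is the extreme case for a given q; an even split would largely cancel in the ratio.

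**The case against.** The strongest case on the other side has five parts.

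- **The weight-loss list serves another purpose.** Item e reads "Consider the impact of people who are on weight loss medications after surgery" and belongs to an optional set of analyses. It does not say that patients without diabetes were on liraglutide before surgery. This stands as a limit on the evidence: no passage shows that such patients exist in the cohort. The item still shows that the SAP regards liraglutide as a drug used for weight.
- **The target population is stated correctly.** It is, so this is an incomplete proxy for the right population. The numbered criteria are nevertheless what the query will apply.
- **Adjustment covers much of the route to bias.** Calendar year is in the propensity model that Aim 2 reuses, a calendar-year sensitivity analysis of remission is planned, and Table 6 lists baseline HbA1c and diabetes medication use as confounders. This stands. A reader might infer that the gap favours whichever procedure was commonest in later years. The SAP reports a temporal trend in procedure use but not its direction, and nothing on liraglutide prescribing by year, so that inference is unsupported.
- **Entry does not guarantee a counted remission.** This stands. A qualifying post-surgery HbA1c is also needed, so near-certain remission among these patients is an assumption.
- **The remedy can drop real cases.** The SAP's Missing Data section says an unrecorded diagnosis cannot be told apart from an absent one. This stands and belongs in the cost.

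Dilution of HbA1c change is a weak argument for the concern, because route 2 deliberately admits medication-controlled patients whose baseline HbA1c is already below 6.5%.

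**Conclusion.** The gap is real on the SAP's own text. The written rule can admit patients outside the stated Aim 2 population and count some of them as remissions, and the existing safeguard covers only one of the two drugs for which the SAP itself names another use.

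Its size cannot be established from the document. Under the assumptions above, the distortion of the hazard ratio is about 1% to 3% for a share of 1% to 2% lying wholly in one procedure group, and less if the share is spread across groups. The comparison between procedures is biased only if liraglutide use without diabetes differs by procedure after adjustment for calendar year and baseline covariates. The document does not support reading this as a demonstrated bias for or against any procedure, or as a reason to distrust the Aim 2 results already obtained. It is a worthwhile, inexpensive tightening of the cohort definition for a primary outcome.

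**What to change.** Reword the note in the Additional Aim 2 Inclusion Criteria along these lines: patients whose only Table 4 drugs are metformin and/or liraglutide are excluded unless they have an ICD-9 code for diabetes (250.x) or an HbA1c of at least 6.5% in the year before surgery.

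Apply the revised rule to the Aim 2 outcomes in Aims 4-6. The SAP indicates that Aim 2 results already exist, so there report the revised rule as a sensitivity analysis, with the number of patients it removes in each procedure group. That count replaces the assumed q.

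The cost is one drug name in an existing rule and query, plus one rerun. The downside is the loss of some truly diabetic, well-controlled liraglutide users with no recorded code, more so at sites with incomplete diagnosis capture. Showing results under both rules lets the reader weigh false inclusion against false exclusion.

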### D. ADDITIONAL AIM 3 INCLUSION CRITERIA

1. For these analyses, eligible patients must be linked to relevant data sources in order to be included in the Aim 3 analysis cohort:
  - State or national death index (mortality outcomes)
  - Payer data/insurance claims (for AE outcomes)
2. Patients must be aged 20 through 79 years of age at time of surgery.
2. Exclude any patient with  $\geq 365$  inpatient hospitalization days in the year prior to surgery.
3. Exclude any patient without male or female sex indicated.

### E. AIMS 4-6 INCLUSION CRITERIA

For these analyses, inclusion criteria for Aims 1, 2, and 3 will be used for the outcomes from those aims. CDRNs will be restricted to those who agree to additional data analyses

### F. ADDITIONAL AIM 5 INCLUSION CRITERIA

People with missing information for race and ethnicity will also be excluded.

### G. AIM 4 AND 6 INCLUSION CRITERIA

No additional inclusion or exclusion criteria above and beyond our original analyses.

## DEFINING THE STUDY OUTCOMES

Study outcomes are defined below in [Table 5](#).

## ANALYTIC PLANS BY AIM

**Descriptive analysis:** The study team will develop a distributed program to create the study cohort based on the eligibility criteria described above. The distributed program will also compare the baseline characteristics of the study cohort with patients who are otherwise eligible for the study but have missing information in key baseline covariates [CI-1, CI-2] (e.g., baseline BMI, and HbA1c among patients with diabetes). The comparison will allow us to assess the representativeness of the study cohort and help explore possible selection bias that can later be addressed in the analysis and interpretation of the study results. This descriptive analysis is different from the study data characterization that will be done prior.

We will characterize and compare eligible patients who undergo the three bariatric procedures in detail. Specifically, we will compare the distributions and missingness of the baseline covariates, the length of follow-up and missingness in post-surgery outcome measures (e.g., changes in BMI and HbA1c among patients with diabetes) [IR-1]. For Aim 5, we will examine differences between patients with and without race and ethnicity information.

A key consideration for observational comparative effectiveness studies is to include only patients who are eligible to receive the alternative treatments being compared. We will assess such “empirical equipoise” by examining the degree of overlap in the distributions of the estimated propensity scores for each of the three pairwise comparisons (described in detail below) [CI-5]. The comparisons will help us identify patients who may have certain characteristics or contraindications that disqualify them from receiving one or more of the three studied bariatric procedures in typical clinical practice. We will restrict the study cohort to patients in the overlapping region of the propensity score distributions as appropriate.

### A. AIM 1 (WEIGHT LOSS AND WEIGHT REGAIN)

#### 1. Primary analysis

The primary analysis will include only patients who meet the eligibility criteria for the study and key baseline covariates (age, sex, and baseline BMI). Table 5 below shows important baseline covariates.

Continuous variables include age, baseline BMI, HbA1c, hospital length of stay during the year prior to surgery, and comorbidity score. Categorical variables include race/ethnicity, insulin use, oral hypoglycemic medication use, CDRN, node site, and year of surgery. We will aggregate comorbidity data into a score derived by combining conditions included in the Charlson and Elixhauser measures that has been externally validated among Medicare enrollees and is predictive of 30-day, 90-day, 180-day and 360-day mortality. This comorbidity score can be efficiently calculated using code from a Mini-Sentinel tool. It includes age, sex, and 37 unique health conditions including both physical and mental health comorbidities. Smoking will be operationalized as current, never, or other.

The outcome of interest will be percentage change in body weight in kilograms (from baseline) at the end of 1 year, 3 years, and 5 years after surgery [CI-3]. As it is a continuous variable, we will inspect the distribution of the variable and transform it as appropriate. We will conduct three pair-wise comparisons – AGB versus RYGB, SG versus RYGB, and AGB vs. SG. For each comparison, we will first use a logistic regression model to estimate the propensity score (PS), which is defined as the probability of receiving the treatment of interest (which can be chosen arbitrarily) in each pairwise comparison given the potential confounders listed in Table 6 plus calendar year. The PS model will be fit at each site. We

will then assess covariate overlap by comparing the PS distributions by surgery group. If patients from different surgery groups differ systematically, we will consider trimming to exclude patients that are very unlikely to be considered for the other surgery option and thus should not be included for comparative effectiveness assessment [CI-5]. We will consider using the linear mixed effects model or the generalized estimating equation model with a link to estimate the effect of surgery on percent weight changes. We will consider different PS-based analyses to adjust for confounding bias, including PS regression, matching, and inverse probability treatment weighting. For PS regression, we create a categorical variable using site-specific PS percentiles (e.g., deciles) and adjust for it in the outcome regression model. In PS matching, for each exposed subject, we use the nearest matching algorithm to find a comparable control whose PS is close to the PS of the exposed subject (e.g., the difference is less than 0.05). We then fit the outcome regression model among the matched population. In inverse probability treatment weighting, we create a weighted pseudo-population consisting of weighted copies of observed data to remove confounding bias and implement the outcome regression model among the pseudo-population. In all models, we will adjust for site in the outcome regression model to account for across-site heterogeneity. Due to the large number of comparisons, we will select a PS analysis that suits our study setting and data best considering the pros and cons of the different PS-based analyses. We will apply the analysis procedure to each imputed dataset. Suppose  $\hat{\theta}_i$  and  $\hat{W}_i \equiv \text{var}(\hat{\theta}_i)$  denote the point and variance estimates for the parameter of interest  $\theta_0$  from the  $i$ th imputed dataset,  $i = 1, 2, \dots, m$ . Then the final point estimate  $\hat{\theta} = \frac{1}{m} \sum_{i=1}^m \hat{\theta}_i$ , the average of the  $m$  complete-data estimates; and the final variance estimate  $\hat{W} = \frac{1}{m} \sum_{i=1}^m \hat{W}_i + \left(1 + \frac{1}{m}\right) \frac{1}{m-1} \sum_{i=1}^m (\hat{\theta}_i - \hat{\theta})^2$  which accounts for both within- and between-imputation variance.

**Handling Pregnancy:** Because pregnancy events have an important impact on body weight. We will ignore any weight measurements that occur during a pregnancy period, as identified by ICD-9 and CPT-4 codes. The pregnancy period will be defined as the 9 months before and 3 months after any code indicating a full-term delivery, pre-term delivery, miscarriage, or abortion procedure.

